4.11.2.3. Evaluation of IM Impact on PK, PD, efficacy and Safety

The impact of IM on PK, PD, and safety will be evaluated by stratifying plasma PK exposure measures (such as plasma peak, trough and post-treatment ISIS 678354 concentrations, etc.), PD biomarker levels, selected clinical efficacy end points and safety measures by subject level ADA data, summarized using typical descriptive statistics, and presented graphically and/or in tables.

ISIS 678354-CS3

Statistical Analysis Plan

Efficacy measures to be stratified by subject level ADA data (e.g., ADACAT) will include but may not be limited to apoC-III and TG levels. Safety measures to be stratified by subject level ADA data will include but may not be limited to AEs, and lab tests for hematology, liver and kidney functions, as appropriate.

Additionally, within subject comparisons on plasma C_{2h} may be conducted in patients with multiple C_{2h} concentrations and presented graphically by subject IM status overall and treatment if deemed appropriate (Wang *et al.* 2016)

Lastly, other stratifications (e.g., based on antibody titer, onset of ADA, subject ADA status at baseline, etc.) of selected PK, efficacy and safety assessments may also be performed if deemed warranted at the discretion of the pharmacokineticist, medical monitor, and/or biostatistician.

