4.11.2.2. Subject Level ADA Data

Subject ADA status overall (ADASTAT) will be defined as 'Positive' status if they have at least one confirmed positive sample result at any time during the treatment or post-treatment evaluation periods; 'Negative' status if all evaluated ADA sample results during the treatment and post-treatment evaluation periods are ADA negative and they have at least one evaluable ADA result collected post-study drug treatment. Otherwise, a study subject will be assigned 'Unknown' ADA status.

Furthermore, subjects with positive overall ADA status may be further classified into different ADA types (ADATYPE) based on their baseline ADA status and change in ADA titer post treatment as described below (Shankar *et al.* 2014):

- Treatment-Emergent ADA: subjects with either treatment-induced ADA or treatment-boosted ADA as described below:
 - o Treatment-Induced ADA: ADA developed de novo (seroconversion) following study drug administration (i.e., formation of ADA any time after the initial drug administration in a subject without pre-existing ADA, i.e., baseline negative ADA).
 - o Treatment-Boosted ADA: pre-existing ADA that were boosted to a higher level following study drug administration (i.e., any time after the initial drug administration the ADA titer is greater than the baseline titer by a factor of 8-fold or more).
- Treatment-Unaffected ADA: pre-existing ADA that were not affected (boosted) following study drug administration (i.e., any time after the initial drug administration the ADA titer is 4-fold or less).
- For patients with negative overall ADA status, ADATYPE would be classified as baseline negative or baseline positive, based on their baseline ADA status.

Other subject level IM parameters to be calculated/defined may include but not limited to:

- ADA category (ADACAT) will include subjects with Negative, Treatment-Unaffected, and Treatment-Emergent ADA status as described above.
- Subject ADA Status at Baseline (ADASTATB): "Positive" if the subject has Week 1 Day 1 pre-dose sample (baseline) tested as confirmed positive; "Negative" if the subject has Week 1 Day 1 pre-dose sample (baseline) tested as negative; "Unknown" if the subject has Week 1 Day 1 pre-dose sample (baseline) unevaluable.
- First day of ADA detected (TFSTADA): i.e., the first day positive ADA sample was observed, will be calculated by: the date of first sample has "positive" sample IM status first dose date +1.

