- Onset of treatment-emergent ADA (ONSETTE): i.e., the first day treatment-emergent ADA positive sample observed, and will be calculated for subjects with treatment-induced ADA and treatment-boosted ADA by:
 - For treatment-induced ADA: the date of first sample has "positive" sample IM status - first dose date +1.
 - For treatment-boosted ADA: the date of the first sample has ADA titer greater than the baseline titer by a factor of 8-fold or more first dose date +1.
- Last Positive ADA Study Day (TLSTADA): defined as the last positive ADA sample observed from the start of study drug treatment and will be calculated by: the date of last sample has "positive" sample IM status first dose date +1.
- Last IM Sampling Study Day (TLSTSAMP): defined as the last ADA sample collected from the start of study drug treatment and will be calculated by: the date of last sample colleted first dose date +1.

- Duration of treatment-emergent ADA (DURTE): i.e., the total duration of treatment-emergent ADA during the study, and will be calculated using the last sample result carried forward. This parameter will be calculated for patients with treatment-induced ADA and treatment-boosted ADA.
- Peak titer (PEAKTIT): the highest titer observed for the subject.
- Time to peak titer (TPEAKTIT): the time to reach peak titer will be calculated by: the date of first peak titer observed first dose date +1.
- Total number of ADA Positive Samples (NOPOSAMP): the total number of ADA samples being confirmed positive for the subject.
- Total number of ADA Samples evaluated (NOADASAMT): the total number of ADA samples being collected and analyzed successfully with reportable results for the subject.

Lastly, subjects with positive ADA status may further be classified as being transient or persistent ADA response, if there are sufficient number of subjects with transient ADA status. Transient and persistent ADA definitions are defined below and based on (Shankar *et al.* 2014):

Transient ADA response:

- Treatment-induced ADA detected only at one sampling time point during the treatment or follow-up observation period (excluding the last sampling time point, which will be considered persistent unless shown to be undetectable at a later time) or

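### The immunogenicity tables group TG, apoC-III and drug levels by an ever-positive ADA label, so late converters count as positive at visits before their first positive sample

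*Combined protocol and SAP*

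**What the plan says.** SAP 4.11.2.2 calls a subject ADA-positive overall with "at least one confirmed positive sample result at any time during the treatment or post-treatment evaluation periods". Treatment-induced ADA has no cut-off in time either: it is "formation of ADA any time after the initial drug administration in a subject without pre-existing ADA". The three-level category is built on these definitions: "ADA category (ADACAT) will include subjects with Negative, Treatment-Unaffected, and Treatment-Emergent ADA status as described above". Each patient gets one fixed value.

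SAP 4.11.2.3 applies subject-level ADA data to the outcomes, stratifying "selected clinical efficacy end points and safety measures by subject level ADA data, summarized using typical descriptive statistics". For lipids: "Efficacy measures to be stratified by subject level ADA data (e.g., ADACAT) will include but may not be limited to apoC-III and TG levels". For safety: "Safety measures to be stratified by subject level ADA data will include but may not be limited to AEs", and laboratory tests are added. PK exposure is stratified in the same way, and SAP 4.11.1 repeats the stratification by immunogenicity status at every scheduled PK time point.

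Timing is not ignored elsewhere. Section 4.11.2.2 derives a start day: "Onset of treatment-emergent ADA (ONSETTE): i.e., the first day treatment-emergent ADA positive sample observed". Section 4.11.2.1 summarises sample-level ADA results by time point. Neither is tied to an outcome in a required analysis. Section 4.11.2.3 allows stratification by onset, and a within-subject comparison of 2-hour concentrations, only at the team's discretion. The second is still displayed by overall status.

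**The concern.** The label at a visit uses samples taken after that visit. A patient whose first positive sample is at Week 37 sits in the positive group for TG at Months 3 and 6, and even for the 2-hour and 4-hour concentrations after the first dose (protocol Appendix C). If ADA weakens the effect only once it is present, these patients contribute unaffected values to the positive group and pull the contrast toward zero.

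Protocol 10.6.4 commits to evaluating how immunogenicity relates to efficacy, safety and PK, and these tables are the planned answer. What is at stake is how far the Month 3, Month 6 and early PK tables can be read as describing patients with antibodies. No confirmatory test is involved.

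**Working it through.** **Plan's own figure.** The documents give no figure for the ADA analysis. The nearest is the sample size in SAP 4.12: SD 46, difference 60 points, 14 per group, two-sided 0.05, 90% power. A noncentral t calculation gives 91.3%, so the figure reproduces. The SD is reused below.

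**Sampling.** Protocol Appendix A places post-dose ADA samples on Days 15, 29, 57, 85, 169, 253 and 365, then 28, 56 and 91 days after end of treatment (Days 393, 421 and 456 for a completer). A completer who enters the OLE has K = 7 samples; one who completes follow-up has K = 10. SAP 4.2.4 expects most patients to enter the OLE. The Month 6 lipid window closes on Day 190.

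- After Month 3: 3 of 7, or 6 of 10.
- After Month 6: 2 of 7, or 5 of 10.
- After Month 12: 0 of 7, or 3 of 10.

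**Dilution.** Let f be the share of ever-positive patients who turn positive only after the endpoint. If ADA acts only once present, labelled contrast = (1 − f) × true contrast. Assume a constant conversion risk h per sample, with k samples up to the endpoint:

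f = 1 − [1 − (1 − h)^k] / [1 − (1 − h)^K]

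Month 6 (k = 5):

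- h = 3%, K = 7: 1 − 0.141/0.192 = 26%. K = 10: 1 − 0.141/0.263 = 46%.
- h = 20%, K = 7: 1 − 0.672/0.790 = 15%. K = 10: 1 − 0.672/0.893 = 25%.

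Loss of contrast over h = 3% to 20%:

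| Endpoint | Enters OLE (K = 7) | Completes follow-up (K = 10) |
|---|---|---|
| Month 3 (k = 4) | 25–40% | 34–56% |
| Month 6 (k = 5) | 15–26% | 25–46% |
| Month 12 (k = 7) | 0% | 11–27% |

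The Month 12 loss falls only on patients who stay for follow-up, expected to be the minority. If all onsets precede Week 27, f at Month 6 is 0.

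**Precision.** The plain-language results summary reports 43 patients on olezarsen (21 + 22). For illustration, pool the doses and assume 13 ever positive and a true 30-point effect. The ever-positive SE is 46 × √(1/13 + 1/30) = 15.3.

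| f | Ever-positive contrast | Positive by endpoint (n) | SE, aligned label |
|---|---|---|---|
| 10% | 27.0 | 12 | 15.6 |
| 25% | 22.5 | 10 | 16.6 |
| 50% | 15.0 | 6 | 20.2 |

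The aligned label keeps the 30 points but at a larger SE.

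**Adverse events.** A simulation assumed no ADA effect, 10% to 30% dropout, about 30% AE risk per year, 80% OLE entry among completers and 5% to 10% conversion per sample. Ever-positive patients showed 1.04 to 1.13 times the crude AE incidence of negatives, because longer observation yields both more samples and more events. Simulated dropouts had no early-termination or follow-up samples; those the protocol provides would narrow the gap in sampling.

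**The case against.** The strongest reply is that the plan offers more than one label, that the analysis is purely descriptive, and that the remedy has faults of its own. Much of this stands. ADACAT separates treatment-unaffected from treatment-emergent ADA, onset and titre are derived, and onset stratification is permitted. There is no test and no decision rule. First detection is also not formation: after Day 169 the next samples are Days 253 and 365, so onset may be recorded up to 84 days (253 − 169) or 112 days (365 − 253) late. Splitting time at onset would put some events that follow seroconversion into the earlier period.

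Two stronger readings are tempting. A reader might infer that patients who leave early, for instance after a hypersensitivity reaction, are under-sampled and so labelled negative. The protocol points against that. Sections 8.5.5 and 8.5.6 trigger ADA tests for persistent or increasing constitutional symptoms and for possible hypersensitivity. Section 8.8.1 provides an early-termination visit and the 13-week follow-up for those who decline landmark visits, and SAP 4.11.2.1 includes early-termination samples. A patient stopping after Week 9 can have Days 15, 29 and 57, the termination visit and three follow-up samples: 7, as many as a completer entering the OLE.

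A reader might also infer that AE associations are always pulled toward no effect. Time on study and event-triggered testing can instead create or inflate an association.

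What the reply does not remove is that the required lipid and PK tables rest on a label without a time limit, and every time-aligned alternative is optional.

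**Conclusion.** The point holds for TG, apoC-III and PK, and it is minor. Patients first positive after a visit are grouped as positive at that visit. The Month 3, Month 6 and early PK contrasts can be diluted, provided that late converters exist and that ADA acts only once present. The Month 6 losses of 15–26% and 25–46% rest on an assumed, constant per-sample risk; the documents give neither ADA incidence nor onset times.

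A reader might take half the samples as falling after Month 6. That holds only for patients completing follow-up; for the expected majority it is 2 of 7. A reader might also infer that the trial will wrongly declare no effect of immunogenicity. The documents contain no rule for such a declaration, and these comparisons lie outside the testing sequence in SAP 4.9.1.3. For AEs and worst-value laboratory summaries, the supportable statement is distortion in either direction.

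**What to change.** In SAP 4.11.2.3, make mandatory a summary of TG and apoC-III at Months 3, 6 and 12, and of each PK sample, by treatment-emergent ADA status up to that assessment: a patient counts as treatment-emergent positive only if ONSETTE is on or before it. For averaged endpoints, state which date applies, for example the last contributing sample. Keep the ever-positive table as a supplement.

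As a supportive descriptive summary, report AEs per person-time before and after ONSETTE, adapting the exposure-adjusted event rate in SAP 4.10.3. Add a note that ONSETTE is first detection and may be up to 84 to 112 days late after Day 169.

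The cost is a few lines of SAP text and some programming, since ONSETTE is already derived. The drawback is few ADA-positive patients at early visits among about 43 treated, so estimates stay imprecise.

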4.11.3. Additional/Exploratory Analysis

4.11.3.1. Percent Change in Fasting TG, apoC-III, apoB-48, and non-HDL-C at Month 3

The following tertiary/exploratory endpoints will be compared between ISIS 678354 treatment group (ISIS 678354 80 mg, ISIS 678354 50 mg) and placebo using an ANCOVA model with the percent change in original scale as the dependent variable, two stratification factors and treatment group as factors, the corresponding log-transformed baseline fasting results as covariates in the FAS. The same multiple imputation method as the primary analysis of the primary endpoint will be used for imputing missing data.

- Percent change in fasting TG from Baseline at Month 3
- Percent change in fasting apoC-III from Baseline at Month 3
- Percent change in fasting apoB-48 from Baseline at Month 3
- Percent change in fasting non-HDL-C from Baseline at Month 3

The change and percent change from Baseline in fasting TG, apoC-III, apoB-48, and non-HDL-C will be summarized by treatment group over time.

4.11.3.2. Treatment Response Rate

The following treatment response rates between ISIS 678354 treatment group (ISIS 678354 80 mg, ISIS 678354 50 mg) and placebo groups will be compared as exploratory analyses using logistic regression with the treatment group, two randomization stratification factors as the factors, and nature log-transformed baseline fasting TG as a covariate in the FAS.

- Proportion of patients who achieve fasting $TG \ge 40\%$ Reduction from Baseline at Months 3 and 12
- Proportion of patients who achieve fasting TG \ge 70% Reduction from Baseline at Months 3 and 12
- Proportion of patients who achieve fasting TG \leq 880 mg/dL at Months 3 and 12 in the subset of FAS with baseline fasting TG > 880 mg/dL
- Proportion of patients who achieve fasting TG \leq 500 mg/dL at Months 3 and 12 in the subset of FAS with baseline fasting TG > 500 mg/dL

Missing values will be handled using the same multiple imputation method as the primary analysis of the primary endpoint.

ISIS 678354-CS3

4.11.3.3. FCS Symptoms

The FCS Symptoms Questionnaire includes 4 items addressing the severity of abdominal pain, physical fatigue, difficulty thinking and diarrhea. These 4 items are administered on a daily basis and ask patients to rate the worst severity of each symptom in the past 24 hours using a 0–10 numeric rating scale. Higher scores denote more severe symptoms.

The daily symptom composite score will be calculated as the average of the non-missing scores across the 4 symptom items. If two or more questions are missing, the symptom composite score will be considered as missing for the day. If one item is missing, then the composite score will be calculated as the average of the 3 non-missing item scores

The data will be mapped to study week based on the visit window specified in Section 4.2.4. The data in the visit window will be averaged and used for summary and analysis. In addition to the weekly average, the highest (worst) response in each week will also be determined and used for summary and analysis. If patients complete less than 4 daily assessments in a week, then the weekly FCS symptom scores will be considered as missing for the week.

Item-level scores and the symptom composite scores, as well as their changes from baseline will be summarized by treatment group and by study week over time using descriptive statistics.

A summary of abdominal pain using the following categories will also be provided: no pain (pain score: 0), mild (pain score: > 0-3), moderate (pain score: > 3-6), or severe (pain score: > 6-10). The frequency and percentage in each category will be tabulated by treatment group and by study week over time.

The change from baseline in the weekly average item and composite scores at the primary analysis time point (average of Weeks 23 to 27) and at Month 12 (average of Weeks 49 to 53) as well as change from baseline in the highest (worst) item and composite scores at the primary analysis time point (worst of Weeks 23 to 27) and at Month 12 (worst of Weeks 49 to 53) will be analyzed using an ANCOVA model with the two stratification factors and treatment group as factors and the corresponding baseline score as a covariate, and will be conducted in the FAS.

The analyses described above will also be repeated using the corresponding FCS symptom collected at the two-week recall administered the first day of screening as the baseline.

The following two exploratory analyses will be performed in the subset of FAS patients who reported any abdominal pain (pain score > 0) at Baseline:

- 1. The first exploratory analysis will be performed to compare the change from Baseline in the weekly average abdominal pain scores at the primary analysis time point (average of Weeks 23 to 27) and at Month 12 (average of Weeks 49 to 53) between the ISIS 678354 treatment groups and placebo group in this subset of patients using an ANCOVA model with the two stratification factors and treatment group as the factors and baseline average abdominal pain score as covariate.
- 2. The secondary exploratory analysis will be performed to compare the change from Baseline in the highest (worst) abdominal pain score at the primary analysis time point (Weeks 23 to 27) and at Month 12 (Weeks 49 to 53) using an ANCOVA model with the two stratification factors and treatment group as factors and worst baseline abdominal pain score as covariate in this subset.

In addition to the analyses described above based on the observed data, the missing values will be imputed. The change from baseline in the weekly average item and composite scores at the primary

analysis time point and at Month 12 as well as change from baseline in the highest (worst) item and composite scores at the primary analysis time point and at Month 12 will be analyzed based on the imputed data using an ANCOVA model with the two stratification factors and treatment group as factors and the corresponding baseline score as a covariate, and will be conducted in the FAS.

The missing values will be imputed as follows:

- For patients with a missing baseline value, their baseline scores will be imputed using the average of non-missing data from other patients in the same stratification category. There are 4 stratification categories:
 - \circ history of pancreatitis = Yes, previous treatment with Volanesorsen = No
 - \circ history of pancreatitis = Yes, previous treatment with Volanesorsen = Yes
 - \circ history of pancreatitis = No, previous treatment with Volanesorsen = No
 - history of pancreatitis = No, previous treatment with Volanesorsen = Yes

In the event of no observed data for imputation, history of pancreatitis will be used as the only classification factor for the purpose of identifying non-missing data for imputation. Additional factors, such as age and gender may be considered to further classify the imputation categories if supported by data.

The item and composite scores will be imputed separately

• The Month 6 (primary analysis time point) score will be calculated from the non-missing weekly scores from Weeks 23 to 27 and the Month 12 score will be calculated from the non-missing weekly scores from Weeks 49 to 53. If all weekly scores during the period are missing, the missing score at the primary analysis time point will be imputed using the data from the week that is the closest to Day 169 and within a ± 30 days window, the missing Month 12 data will be imputed using the data from the week that is the closest to the Day 351 and within a ± 30 days window. If 2 or more visits with equal distance, then the average or worst will be used. The item and composite scores will be imputed separately.

ISIS 678354-CS3

Statistical Analysis Plan

The tables below list the summaries and analyses to be performed for the FCS symptom item and composite scores

Observed Data			
Endpoint	Baseline	Post-baseline	Analysis
Average FCS Symptom – item score and composite score	Baseline is defined as the average during the screening period and up to Day 1. If all assessments during the period are missing, the baseline will be considered as missing	Weekly average. If a patient has less than 4 assessments in a week, the weekly score will be considered as missing	 Descriptive statistics of score, change and percent change over time in the FAS Frequency of patients by abdominal pain category (no pain, mild, moderate and severe) over time in the FAS
		Month 6 (Primary analysis time point) - average of Weeks 23 to 27 Month 12 -average of Weeks 49 to 53	 Descriptive statistics of score, change and percent change at Month 6 and Month 12 in the FAS ANCOVA model of change from baseline with the two stratification factors and treatment group as factors, and the corresponding baseline score as a covariate in the FAS Descriptive statistics of abdominal pain score, change and percent change at Month 6 and Month 12 in the subset of FAS patients who reported any abdominal pain (pain score > 0) at Baseline ANCOVA model of change from baseline in abdominal pain score with the two stratification factors and treatment group as factors and the baseline score as a covariate in the subset of FAS patients who reported any abdominal pain (pain score > 0) at Baseline
	Baseline is defined as the single observation collected at the first day of screening with a two-week recall	Weekly average. If a patient has less than 4 assessments within a week, the weekly score will be considered as missing	Descriptive statistics of score, change and percent change over time in the FAS

ISIS 678354-CS3

Observed Data			
Endpoint	Baseline	Post-baseline	Analysis
Average FCS Symptom – item score and composite score (Continued	Baseline is defined as the single observation collected at the first day of screening with a two-week recall (Continued)	Month 6 (Primary analysis time point) - average of Weeks 23 to 27 Month 12 -average of Weeks 49 to 53	 Descriptive statistics of score, change and percent change at Month 6 and Month 12 in the FAS ANCOVA model of change from baseline with the two stratification factors and treatment group as factors and the corresponding baseline score as a covariate in the FAS
Worst FCS Symptom – item score and composite score	Baseline is defined as the worst during the screening period and up to Day 1. If all assessments during the period are missing, the baseline will be considered as missing	Weekly worst. If a patient has less than 4 assessments in a week, the weekly score will be considered as missing	 Descriptive statistics of score, change and percent change over time in the FAS Frequency of patients by abdominal pain category (no pain, mild, moderate and severe) over time in the FAS
		Month 6 (Primary analysis time point) - worst of Weeks 23 to 27	 Descriptive statistics of score, change and percent change at Month 6 and Month 12 in the FAS
		Month 12 -worst of Weeks 49 to 53	2. ANCOVA model of change from baseline with the two stratification factors and treatment group as factors and the corresponding baseline score as a covariate on FAS
			 Descriptive statistics of abdominal pain score, change and percent change at Month 6 and Month 12 in the subset of ITT patients who reported any abdominal pain (pain score > 0) at Baseline
			 ANCOVA model of change from baseline in abdominal pain score with the two stratification factors and treatment group as factors and the baseline score as a covariate in the subset of ITT patients who reported any abdominal pain (pain score > 0) at Baseline

ISIS 678354-CS3

Observed Data			
Endpoint	Baseline	Post-baseline	Analysis
Worst FCS Symptom – each item score and composite score (Continued	Baseline is defined as the single observation collected at the first day of screening with a two-week recall	Weekly worst. If a patient has less than 4 assessments in a week, the weekly score will be considered as missing	Descriptive statistics of score, change and percent change over time in the FAS
		Month 6 (Primary analysis time po-nt) - worst of Weeks 23 to 27	1. Descriptive statistics of score, change and percent change at Month 6 and Month 12 in the FAS
		Month 12 -worst of Weeks 49 to 53	2. ANCOVA model of change from baseline with the two stratification factors and treatment group as factors and the corresponding baseline score as a covariate in the FAS

Imputed Data			
Endpoint	Baseline	Post-baseline	Analysis
Average FCS Symptom – item score and composite score	Baseline is defined as the average during the screening period and up to Day 1. If all assessments during the period are missing, the baseline will be considered as missing. Missing baseline will be imputed using the average of non-missing data from other patients in the same stratification category	Month 6 (Primary analysis time point) - average of Weeks 23 to 27 Month 12 -average of Weeks 49 to 53. If all weekly scores during the period are missing, the missing Month 6 score will be imputed using the data from the week that is the closest to Day 169 and within $a \pm 30$ days window, the missing Month 12 data will be imputed using the data from the week that is the closest to the Day 351 and within $a \pm 30$ days window. If 2 or more visits with equal distance, then the average will be used.	 Descriptive statistics of score, change and percent change at Month 6 and Month 12 in the FAS ANCOVA model of change from baseline with the two stratification factors and treatment group as factors and the corresponding baseline score as a covariate in the FAS

ISIS 678354-CS3

Imputed Data			
Endpoint	Baseline	Post-baseline	Analysis
Average FCS Symptom – item score and composite score (Continued)	Baseline is defined as the single observation collected at the first day of screening with a two-week recall Missing baseline will be imputed using the average of non-missing data from other patients in the same stratification category	Month 6 (Primary analysis time point) - average of Weeks 23 to 27 Month 12 -average of Weeks 49 to 53. If all weekly scores during the period are missing, the missing Month 6 score will be imputed using the data from the week that is the closest to Day 169 and within a ± 30 days window, the missing Month 12 data will be imputed using the data from the week that is the closest to the Day 351 and within a ± 30 days window. If 2 or more visits with equal distance, then the average will be used.	 Descriptive statistics of score, change and percent change at Month 6 and Month 12 in the FAS ANCOVA model of change from baseline with the two stratification factors and treatment group as factors and the corresponding baseline score as a covariate in the FAS
Worst FCS Symptom – each item score and composite score	Baseline is defined as the worst during the screening period and up to Day 1. If all assessments during the period are missing, the baseline will be considered as missing Missing baseline will be imputed using the average of non-missing data from other patients in the same stratification category	Month 6 (Primary analysis time point) - worst of Weeks 23 to 27 Month 12 -worst of Weeks 49 to 53 If all weekly scores during the period are missing, the missing Month 6 score will be imputed using the data from the week that is the closest to Day 169 and within $a \pm 30$ days window, the missing Month 12 data will be imputed using the data from the week that is the closest to the Day 351 and within $a \pm 30$ days window. If 2 or more visits with equal distance, then the worst will be used.	 Descriptive statistics of score, change and percent change at Month 6 and Month 12 in the FAS ANCOVA model of change from baseline with the two stratification factors and treatment group as factors and the corresponding baseline score as a covariate in the FAS

ISIS 678354-CS3

